## 7.2. Primary Endpoint

There is no single primary endpoint for this study.

## 7.3. Word Recognition in Quiet

Word Recognition is measured using the incidence of correctly recognized words from recorded consonant-nucleus-consonant (CNC) word lists. The WR test consists of 50 words and the number of and assessed percentage of correctly recognized words out of 50 will be recorded. If all 50 words are not assessed in each ear, the WR test score will not be calculated.

WR will be performed at Screening, Day 15, 60, 90, 150, and 210 visits. Testing will be performed at 30 dB sensation level (SL) regarding the pure tone average of 0.5, 1, and 2 kHz

at Screening. Word lists will be rotated at each visit. Additional details can be found in the study Audiology Manual of Procedures.

Baseline scores for analysis will be computed from the Screening visit. There will be no imputation for missing scores.

#### 7.3.1. Number of recognized words

- *Computation of the Endpoint*

At each visit and by ear (left, right), the number of words classified as correctly recognized out of 50 will be recorded. Left and right ears will be mapped to treated and untreated for analysis, as described in Section 3.

In subjects in the FAS with hearing loss in both ears per the Targeted Hearing Loss History CRF page, the ratio of the number of recognized words for treated ear versus untreated ear will be computed.

- *Analysis of the Endpoint*

The number of recognized words will be summarized descriptively for treated and untreated ears separately by visit and treatment group for subjects in the FAS.

Treatment group comparisons will be performed using the approach described in Section 7.3.4 for subjects in the FAS. The covariance structure (UN or AR(1)) that provides the best model fit for the relative percent change from baseline in percentage of recognized words, as described in Section 7.3.4, will be implemented with a repeated statement in SAS.

The ratio of the number of recognized words for treated ears versus untreated ears will be summarized descriptively by visit and treatment group for all subjects in the FAS, subjects in the FAS with bilateral hearing loss, and subjects in the FAS without bilateral hearing loss.

- *Sensitivity Analyses of the Endpoint*

The analyses will be repeated for subjects in the PPAS.

If there are any dosing administrations errors such that a not qualified ear is treated, the descriptive summaries by treated and untreated ears will be repeated for subjects in the FAS including all treated and untreated ear data.

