**Study Design:**

This is a Phase 2a, prospective, randomized, double-blind, placebo-controlled, single and repeat-dose, multicenter, exploratory efficacy study of FX-322, administered by intratympanic injection, in adults with stable sensorineural hearing loss (no changes in air conduction greater than 10 dB at a single frequency or greater than 5dB at two contiguous frequencies from the prior audiogram to the Screening audiogram).

The study will have 3 phases: Screening, Treatment, and Follow-up.

**Screening:** Can occur up to 30 days prior to study drug administration (Baseline/Treatment Day 1). All subjects will be screened to determine study eligibility. As part of recording the medical history of subjects, concurrent use of hearing aids during the study will be documented. All subjects will return for the Baseline visit and evaluated to ensure they continue to meet appropriate inclusion/exclusion criteria applicable at that visit.

**Baseline/Treatment:** Approximately 96 subjects are planned to be enrolled in this study. The subjects will be randomized to receive FX-322 or placebo according to the different treatment group schedules listed below:

| Group Dosing Schedule |                      |              |              |               |               |
|------------------------------|----------------------|--------------|--------------|---------------|---------------|
| Treatment Group       | # of Subjects | Day 1 | Day 8 | Day 15 | Day 21 |
| 1                            | 24                   | FX-322       | Placebo      | Placebo       | Placebo       |
| 2                            | 24                   | FX-322       | FX-322       | Placebo       | Placebo       |
| 3                            | 24                   | FX-322       | FX-322       | FX-322        | FX-322        |
| 4                            | 24                   | Placebo      | Placebo      | Placebo       | Placebo       |

Once a subject has been identified as meeting all inclusion/exclusion criteria, the qualifying ear with the worse hearing (ear with the worst Screening pure tone average) will be selected, unless a rationale exists to treat the other ear (e.g. the worse hearing ear does not meet the study criteria). The study treatment or placebo will be administered on Day 1, Day 8, Day 15, and Day 21. The placebo will be matched to FX-322 in consistency and color.

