### **8.4.2 Inclusion Criteria**

To be eligible for study entry subjects must satisfy all of the following criteria:

1. Subject has read and voluntarily signed the Informed Consent Form (ICF) after all questions have been answered and prior to any study-mandated procedure.
2. Adult aged 18-65 years inclusive.
3. Established diagnosis of stable sensorineural hearing loss by standard audiometric measures for  $\geq 6$  months prior to the Screening visit (no changes in air conduction greater than 10 dB at a single frequency or greater than 5dB at two contiguous frequencies from the prior audiogram to the Screening audiogram in the study ear).
4. Documented medical history consistent with hearing loss being caused by noise exposure or sudden sensorineural hearing loss (documented audiogram at least 6 months prior to screening required).
5. A pure tone average of 26-70 dB at 500Hz, 1000Hz, 2000Hz, and 4000Hz in the ear to be injected.
6. Subjects with a 15% - 85% correct score on Word Recognition test (8 – 42 words correct out of 50) at Screening in the study ear.
7. Ability to communicate well with the Investigator and is willing to comply with and complete all the study procedures.
8. Female subjects must be of non-childbearing potential or will need to utilize two methods of highly effective contraception during the study participation (e.g. hormonal contraception or an intrauterine device and condoms) or remain abstinent. Male subjects

should use condoms with spermicide during the course of the study or remain abstinent. Subjects should not donate sperm or ova during the study period.

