**Table 7-2 Efficacy Variables and Analysis Methods**

Efficacy Endpoint	Analysis Method(s)	Section
Word Recognition in Quiet		7.3
Number of recognized words	
 
• Descriptive summary for treated and untreated ears.
 
• MMRM in treated ears.
 
• Risk ratios of treated ears to untreated ears for all subjects, subjects with bilateral hearing loss, and subjects without bilateral hearing loss.
 
	7.3.1
Percentage of recognized words	
 
• Descriptive summary for treated and untreated ears.
 
• MMRM in treated ears.
 
• Sensitivity: Descriptive summary for treated ears by site.
 
	7.3.2
Absolute percent change from baseline in percentage of recognized words	
 
• Descriptive summary for treated and untreated ears.
 
• Line graphs (with standard error bars) for observed means for treated ears.
 
• Line graphs (with standard error bars) for adjusted (least squares) means for treated ears.
 
• MMRM in treated ears.
 
• Sensitivity: Descriptive summary for treated ears by site.
 
	7.3.3
Relative percent change from baseline in percentage of recognized words	
 
• Descriptive summary for treated and untreated ears.
 
• Line graphs (with standard error bars) for observed means for treated ears.
 
• Line graphs (with standard error bars) for adjusted (least squares) means for treated ears.
 
• MMRM in treated ears.
 
• Sensitivity: Descriptive summary for treated ears by site.
 
	7.3.4
Improvement $\geq 10\%$ (5 words) in percentage of recognized words	
 
• Descriptive summary for treated ears.
 
• GEE in treated ears.
 
	7.3.5
Arcsine-transformed WR	
 
• Descriptive summary for treated ears.
 
• MMRM in treated ears.
 
	7.3.6
WR categories	
 
• Descriptive summary for treated ears.
 
• Bar charts for treated ears.
 
	7.3.7

Efficacy Endpoint	Analysis Method(s)	Section
Shift in WR categories	
 
Descriptive summary for treated ears.
 
	7.3.8

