#### 7.4.2. Percentage of recognized words

- *Computation of the Endpoint*

Using the number of recognized words in Section 7.4.1, the percentage of recognized words will be computed for each signal-to-noise ratio by visit as the number of recognized words divided by 10 and multiplied by 100, separately for each ear. The percentage of recognized words overall by visit will be computed as the number of recognized words divided by 70 and multiplied by 100, separately for each ear.

- *Analysis of the Endpoint*

The percentage of recognized words at each signal-to-noise ratio and overall will be summarized descriptively for treated and untreated ears using the approach described in Section 7.4.1 for subjects in the FAS.

Line graphs (with standard error bars) will be created for the observed percentage of recognized words at each signal-to-noise ratio for treated ears by visit and treatment group for subjects in the FAS. The signal-to-noise ratio will be plotted on the x-axis and the

percentage of recognized words will be plotted on the y-axis. There will be separate lines for each treatment group and possibly separate plots for each visit. All treatment groups and visits may be included in a single plot, if the lines are not too crowded.

Treatment group comparisons for the percentage of recognized words overall will be performed using the approach described in Section 7.4.4 for subjects in the FAS. The covariance structure (UN or AR(1)) that provides the best model fit for the relative percent change from baseline in percentage of recognized words, as described in Section 7.4.4, will be implemented with a repeated statement in SAS. Treatment group comparisons will not be performed for each signal-to-noise ratio.

- *Sensitivity Analyses of the Endpoint*

With the exception of the line graphs, the analyses will be repeated for subjects in the PPAS.

If there are any dosing administrations errors such that a not qualified ear is treated, the descriptive summaries by treated and untreated ears will be repeated for subjects in the FAS including all treated and untreated ear data.

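### The treated-to-untreated ear word ratio is computed for subjects with bilateral loss but reported for three populations, and the SAP has no rule for a zero or near-zero untreated-ear score

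*SAP*

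**What the plan says.** The computation paragraph of SAP 7.3.1 (word recognition in quiet, WR) defines the ratio for one population: "In subjects in the FAS with hearing loss in both ears per the Targeted Hearing Loss History CRF page, the ratio" of recognised words, treated ear over untreated ear, is computed. The analysis paragraph of the same section plans descriptive summaries, at each visit and in each arm, for three populations: "for all subjects in the FAS, subjects in the FAS with bilateral hearing loss, and subjects in the FAS without bilateral hearing loss". SAP 7.4.1 has the same pair of statements for WIN. The WR entry in Table 7-2 lists "Risk ratios of treated ears to untreated ears for all subjects, subjects with bilateral hearing loss, and subjects without bilateral hearing loss", and the WIN entry has a near-identical line.

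Three other places bear on the denominator:

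- Protocol 8.4.2, criterion 6, sets the WR entry range: "8 – 42 words correct out of 50) at Screening in the study ear". It sets no range for the other ear, and no criterion uses WIN.
- The Protocol synopsis has the worse qualifying ear treated "unless a rationale exists to treat the other ear (e.g. the worse hearing ear does not meet the study criteria").
- SAP 7.3 says of WR: "There will be no imputation for missing scores". Nothing in the SAP covers a zero denominator.

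For WIN, SAP 7.4.1 records counts at each signal-to-noise ratio and overall, without saying which one the ratio uses. SAP 7.4.2 shows that one level has ten words: "the number of recognized words divided by 10 and multiplied by 100, separately for each ear".

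**The concern.** The rule that creates the variable and the rule that reports it name different populations. A programmer must either override the computation sentence or deliver one empty table and one duplicate. The same applies to the Per Protocol repeat that both sections call for.

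The form of the measure adds a second problem. A ratio of two word counts has no value when the untreated ear scores 0 and swings widely when it scores a few words. The plan does not say what happens to such subjects.

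This is the only planned contrast that pairs the two ears within a subject. The untreated ear is tested at the same audiology visits as the treated ear, so a well-defined paired measure would be a useful check on changes common to both ears.

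The Table 7-2 label is also wrong. The quantity is a ratio of word counts within a subject, not a ratio of risks.

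**Working it through.** The plan gives no numeric result for this ratio, so there is no figure to reproduce. The check compares the text and then works the arithmetic of the ratio.

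**1. Populations (SAP 7.3.1, 7.4.1, Table 7-2)**

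| Reported population | Subjects with a computed ratio under the literal rule |
|---|---|
| All FAS | Bilateral subjects only, so the same as the next row |
| FAS with bilateral loss | Bilateral subjects |
| FAS without bilateral loss | None |

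**2. Range of the denominator**

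- Criterion 6: 15% of 50 is 7.5, rounded up to 8 words; 85% of 50 is 42.5, rounded down to 42. This agrees with the stated 8 to 42 and applies to the study ear at Screening.
- The untreated ear may score anywhere from 0 to 50. A worse ear with 0 to 7 words fails criterion 6 and can then become the untreated ear.

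**3. Size of the ratio**

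Ratio = treated words / untreated words. With an assumed 20 treated words:

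- 20/7 = 2.9
- 20/4 = 5
- 20/2 = 10
- 20/1 = 20
- 20/0 is undefined

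**4. Effect on a group summary**

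Assume a group of 24 (the planned size) in which 23 ratios equal 0.8:

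- One ratio of 10: mean = (23 × 0.8 + 10)/24 = 28.4/24 = 1.18
- One ratio of 20: mean = (23 × 0.8 + 20)/24 = 38.4/24 = 1.60
- The median is 0.80 in both cases.

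**5. Chance of a zero denominator**

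P(0) = (1 − p)^n, where p is an assumed probability that the untreated ear recognises a word:

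| p | WR, n = 50 | WIN overall, n = 70 | One WIN level, n = 10 |
|---|---|---|---|
| 0.05 | 7.7% | 2.8% | 60% |
| 0.10 | 0.5% | 0.06% | 35% |
| 0.20 | about 0% | about 0% | 11% |

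The last column matters only if the WIN ratio is taken at each signal-to-noise level, which SAP 7.4.1 leaves open.

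**6. Test-retest noise in the WR ratio**

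This simulation used independent binomial scores on 50 words, with an assumed treated-ear probability of 0.5:

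| Untreated-ear probability | Central 95% of defined ratios | Undefined |
|---|---|---|
| 0.80 | 0.44 to 0.83 | 0% |
| 0.50 | 0.67 to 1.50 | 0% |
| 0.10 | 2.4 to 21 | 0.5% |
| 0.04 | 4.5 to 30 | 13% |

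The ratio behaves acceptably when the untreated ear is the better one and poorly when that ear scores very low.

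**The case against.** The strongest reply is that this is a wording slip in a minor descriptive table. The analysis paragraphs and Table 7-2 agree on three populations, and only the computation sentence in each section is out of line. The ratio is not modelled or tested. SAP 7.2 names no single primary endpoint, and SAP 7.1.4 treats all p-values as descriptive. The treated-ear efficacy models are untouched. All of this stands, and it limits the weight of the point.

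A reader might infer four stronger things that the documents do not support.

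- *The ratio cannot be tabulated for two of its three populations.* The all-subjects table can be filled; it merely repeats the bilateral one. Only the non-bilateral table is empty.
- *Extreme ratios will drive the results.* The treated ear is normally the worse one, so the denominator is usually the larger count. Very small denominators arise mainly when the better ear is treated. An ear can also fail entry for reasons unrelated to WR, such as pure tone average, conductive loss or a membrane disorder. No document says how often a non-qualifying worse ear has a very low WR score. SAP Section 3 also reports the median, minimum and maximum, so an outlier would be visible.
- *The untreated ear is otherwise unused.* SAP 7.3.3, 7.3.4, 7.4.3 and 7.4.4 already summarise change from Screening in untreated ears by visit and group. With the same subjects in both summaries, the mean paired difference is simply the difference of those two means. The paired standard deviation and the split by bilateral loss would be new.
- *The ratio shows only which ear was chosen.* Its level does carry the baseline gap between ears. However, it is summarised by visit, Screening is a testing visit, and the ear-selection rule is the same in every randomised group. Shifts from Screening and differences from placebo can still be read.

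The mismatch of populations, the missing rule for a zero denominator and the wrong label remain.

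**Conclusion.** The point holds in a limited form. The population contradiction is in the current SAP text for both WR and WIN and needs no assumption beyond a literal reading: one table is empty and one is a duplicate.

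The instability is a real possibility that the entry criteria allow and the SAP does not address. It is probably uncommon. The means of 1.18 and 1.60 rest on assumed values (23 ratios of 0.8 and one outlier), and the unchanged median of 0.80 shows that the harm is confined to the mean and standard deviation. The exposure would be much larger if the WIN ratio were taken at each ten-word level.

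No model, test or decision depends on the ratio. The change is still worth making: the difference in change is always defined when both ears are tested, removes the baseline gap between ears and fits all three populations.

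**What to change.** In SAP 7.3.1 and 7.4.1, replace the ratio. For every FAS subject with both ears tested, compute the within-subject difference in absolute percentage-point change from Screening, treated minus untreated, using the overall score for WIN. Summarise it by visit and treatment group for all subjects, those with bilateral loss and those without. The existing Section 3 exclusion of untreated-ear data after a wrong-ear injection would continue to apply.

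If the ratio is kept:

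- compute it for all FAS subjects with both ears tested, with bilateral loss as a subgroup;
- report the median and the number of subjects with a zero denominator;
- state that the WIN ratio uses the overall score.

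In either case, replace the term risk ratio in both Table 7-2 entries (WR and WIN) with a description of the quantity actually reported.

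The cost is minor SAP wording and programming. The absolute changes are already derived for both ears in SAP 7.3.3 and 7.4.3, so the new variable is one subtraction on existing data.

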#### 7.3.2. Percentage of recognized words

- *Computation of the Endpoint*

Using the number of recognized words in Section 7.3.1, the percentage of recognized words will be computed by visit as the number of recognized words divided by 50 and multiplied by 100, separately for each ear.

- *Analysis of the Endpoint*

The percentage of recognized words will be summarized descriptively for treated and untreated ears using the approach described in Section 7.3.1 for subjects in the FAS.

Treatment group comparisons will be performed using the approach described in Section 7.3.4 for subjects in the FAS. The covariance structure (UN or AR(1)) that provides the best model fit for the relative percent change from baseline in percentage of recognized words, as described in Section 7.3.4, will be implemented with a repeated statement in SAS.

- *Sensitivity Analyses of the Endpoint*

The analyses will be repeated for subjects in the PPAS.

The possible presence of site-to-site heterogeneity will be evaluated by descriptively summarizing the percentage of recognized words for treated ears by site, visit, and treatment group for subjects in the FAS.

If there are any dosing administrations errors such that a not qualified ear is treated, the descriptive summaries by treated and untreated ears will be repeated for subjects in the FAS including all treated and untreated ear data.

### 7.3.3. Absolute percent change from baseline in percentage of recognized words

- *Computation of the Endpoint*

The absolute percent change from baseline to each post-baseline visit in percentage of recognized words will be computed as  $100 * [(w/50) - (b/50)]$  where “w” is the frequency of words recognized at the post-baseline visit and “b” is the frequency of words recognized at baseline.

- *Analysis of the Endpoint*

The absolute percent change from baseline in percentage of recognized words will be summarized descriptively for treated and untreated ears using the approach described in Section 7.3.1 for subjects in the FAS.

Line graphs (with standard error bars) will be created for the adjusted (least squares) mean absolute percent change from baseline in percentage of recognized words for treated ears by post-baseline visit and treatment group for subjects in the FAS. Post-baseline visit will be plotted on the x-axis and the adjusted (least squares) mean absolute percent change from baseline in percentage of recognized words for treated ears will be plotted on the y-axis. Each treatment group will be presented as a separate line in the plot. The line graphs will be repeated for the observed mean absolute percent change from baseline in percentage of recognized words for treated ears.

Treatment group comparisons will be performed using the approach described in Section 7.3.4 for subjects in the FAS. The covariance structure (UN or AR(1)) that provides the best model fit for the relative percent change from baseline in percentage of recognized words, as described in Section 7.3.4, will be implemented with a repeated statement in SAS.

- *Sensitivity Analyses of the Endpoint*

With the exception of the line graphs, the analyses will be repeated for subjects in the PPAS.

The possible presence of site-to-site heterogeneity will be evaluated using the approach described in Section 7.3.2 for subjects in the FAS.

If there are any dosing administrations errors such that a not qualified ear is treated, the descriptive summaries by treated and untreated ears will be repeated for subjects in the FAS including all treated and untreated ear data.

#### 7.3.4. Relative percent change from baseline in percentage of recognized words

- *Computation of the Endpoint*

The relative percent change from baseline to each post-baseline visit in percentage of recognized words will be computed as  $100 * [(w-b)/b]$  where “w” is the frequency of words recognized at the post-baseline visit and “b” is the frequency of words recognized at baseline.

- *Analysis of the Endpoint*

The relative percent change from baseline in percentage of recognized words will be summarized descriptively for treated and untreated ears using the approach described in Section 7.3.1 for subjects in the FAS.

Line graphs (with standard error bars) for the adjusted (least squares) means and observed means will be created using the approach described in Section 7.3.3 for subjects in the FAS.

In treated ears only for subjects in the FAS, treatment group comparisons for the relative percent change from baseline in percentage of recognized words will be analyzed using a mixed-effect, repeated measures model using fixed covariates for treatment group, WR score at baseline (<50% versus >=50%), etiology of hearing loss (SSNHL versus NIHL), visit, and interaction between visit and treatment group. Separate models will be fit specifying UN and AR(1) covariance structures (implemented with a repeated statement in SAS). The covariance structure providing the lowest corrected Akaike’s Information Criteria (AICc) and Bayesian Information Criteria (BIC) values from the model will be implemented for the relative percent change from baseline and all other WR endpoints. The treatment group differences analyzed will be between each FX-322 group (including the pooled FX-322 group) versus placebo, and comparisons between the individual FX-322 groups (excluding the pooled FX-322 group). Comparisons will be made by visit (e.g., estimated Least squares (LS) Mean differences by visit) and overall (e.g., Type III Sums of Squares).

- *Sensitivity Analyses of the Endpoint*

With the exception of the line graphs, the analyses will be repeated for subjects in the PPAS.

The possible presence of site-to-site heterogeneity will be evaluated using the approach described in Section 7.3.2 for subjects in the FAS.

If there are any dosing administrations errors such that a not qualified ear is treated, the descriptive summaries by treated and untreated ears will be repeated for subjects in the FAS including all treated and untreated ear data.

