## **7.2 Endpoints**

### **Efficacy Endpoint(s)**

- Mean changes from Screening in:
  - Word Recognition in quiet (WR)
  - Words-In-Noise testing (WIN)
  - Standard Pure Tone Audiometry (air 0.25-8 kHz; bone 0.5-4 kHz)

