#### **14.1.5 Efficacy Exploration**

Efficacy endpoints will be summarized descriptively at each study timepoint including baseline. Calculations will include the observed data at each timepoint, and if relevant, the change from baseline. For continuous endpoints means, medians, standard deviations, minimums and maximum will be provided. For categorical endpoints the number and percent of subjects within each category will be calculated. Tabulations for selected endpoints will be presented by subgroups such as age, study site, duration of hearing loss, smoking status, and stratification factors used at randomization. Details will be provided in the SAP. For descriptive analyses, subjects with missing data will be excluded for a particular calculation.

For questionnaires, the analysis will follow the instructions for scoring and handling of missing data appropriate for the particular instrument.

Inferential statistical methods examining continuous endpoints will be examined via a Mixed Model for Repeated Measures (MMRM). Analyses will include pairwise contrasts and dose response. Inferential analyses for categorical endpoints will be analysed using univariate methods and/or Generalized Linear Mixed Models (GLMM). When appropriate, models will include adjustments for baseline as well as the stratification factors used at randomization. Departures of these models from the statistical assumptions will be assessed and alternative approaches maybe employed. Additionally, univariate models such as Analysis of Covariance and/or count models examining single timepoints of interest may also be examined. General methods for handling missing data for inferential analyses are described below (Section 14.2).

The inferential analyses will not be adjusted for multiple endpoints; however, for a given endpoint, adjusted p-values for pairwise comparisons to a control will be provided where

relevant along with the unadjusted p-values. Unadjusted 95% confidence intervals will also be provided. In some circumstances, adjusted confidence intervals may be calculated.

Efficacy endpoints will be analysed using the FAS. Further details regarding the exploratory analysis of efficacy will be outlined in the SAP.

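### The word recognition (WR) models adjust for baseline only as below versus at or above 50%; adding the measured Screening score would sharpen the number, percentage and arcsine analyses by an amount the documents cannot fix

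*SAP*

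**What the plan says.** SAP 7.3.4 gives the WR model in full for relative change from baseline. It is fitted "using fixed covariates for treatment group, WR score at baseline" and further terms. Those other than treatment, visit and their interaction are "WR score at baseline (<50% versus >=50%), etiology of hearing loss (SSNHL versus NIHL"). No WR model contains the measured baseline score.

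SAP 7.3.1 (number of words) then states: "Treatment group comparisons will be performed using the approach described in Section 7.3.4 for subjects in the FAS". Sections 7.3.2 (percentage), 7.3.3 (absolute change) and 7.3.6 (arcsine) refer back in the same way.

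Protocol 14.1.5 says: "When appropriate, models will include adjustments for baseline as well as the stratification factors used at randomization". It leaves further detail to the SAP. SAP Section 11, which lists departures from the protocol, mentions only multiplicity adjustment.

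The protocol frames its efficacy endpoints as "Mean changes from Screening in" WR, WIN and audiometry. Entry is limited by inclusion criterion 6: "Subjects with a 15% - 85% correct score on Word Recognition test", given there as 8-42 words of 50.

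**The concern.** A two-level category is a coarse stand-in for a score that can take 35 values among eligible subjects. Below 50% there are 17 possible scores (8-24 words), and at or above 50% there are 18 (25-42 words). For an endpoint analysed as a level, most of those differences carry forward to follow-up and remain in the residual.

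Two things follow for 7.3.1, 7.3.2 and 7.3.6. The intervals are wider than they need be. Any chance baseline difference between arms within a category also passes into the treatment contrast at nearly full size. The level analyses can then disagree with the change analysis of the same words, and SAP 7.2 names no single primary endpoint that would settle which to read.

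**Working it through.** **What can be reproduced.** The sample size has no formal basis (SAP 2.4), and the documents give no WR SD or baseline/follow-up correlation, so there is no planned variance to rebuild. The only noise figures are the 95% critical differences in SAP 14.1. A double-arcsine calculation with variance 1/(n + 0.5) and n = 50 returns the chart rows for scores 20, 30, 50, 70 and 80 exactly (8-36, 14-48, 32-68, 52-86, 64-92). Binomial word-list noise is therefore a fair floor.

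**How much baseline variance the category carries.** Assume scores spread evenly over 16, 18, ..., 84%.
- Total variance: 4 × (35² − 1)/12 = 408.
- Within category: 4 × (17² − 1)/12 = 96 below 50%, and 4 × (18² − 1)/12 = 107.7 above. Weighted: (17 × 96 + 18 × 107.7)/35 = 102.
- Share carried: k = 1 − 102/408 = 0.75. For a normal distribution cut at its median, k = 2/π = 0.64.

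**Closed form.** With correlation r between baseline and follow-up, the residual variance with category and score, divided by that with category alone, is (1 − r²)/(1 − k r²).
- r = 0.7: 0.51/0.688 = 0.74 (normal); 0.51/0.6325 = 0.81 (even).
- r = 0.8: 0.36/0.593 = 0.61; 0.36/0.52 = 0.69.
- A ratio of 0.50 needs r = √(0.5/(1 − k/2)) = 0.86 (normal) or 0.89 (even). With an even spread, word-list noise alone caps r at about 0.91.

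**Simulation.** Binomial 50-word scores, entry range 16-84%, 1,000,000 subjects per scenario. Baseline shape, SD of true change and extra session-to-session SD are assumptions. Detectable difference = (1.96 + 0.84) × √V × √(2/24), for two-sided 0.05 and 80% power (also assumed). The last column is the SD that within-category baseline imbalance adds to one 24 v 24 contrast: √((V1 − V2) × 2/24).

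| Baseline shape; change SD; session SD (points) | V1: category only | V2: category + score | V2/V1 | Detectable difference | Imbalance SD |
|---|---|---|---|---|---|
| Even; 0; 0 | 177 | 82 | 0.46 | 10.8 to 7.3 | 2.8 |
| Even; 10; 0 | 270 | 177 | 0.66 | 13.3 to 10.8 | 2.8 |
| Upper-weighted; 10; 0 | 249 | 177 | 0.71 | 12.8 to 10.8 | 2.4 |
| Mid-weighted; 10; 0 | 235 | 182 | 0.77 | 12.4 to 10.9 | 2.1 |
| Mid-weighted; 10; 6 | 281 | 238 | 0.85 | 13.6 to 12.5 | 1.9 |
| Clustered; 10; 0 | 208 | 180 | 0.86 | 11.7 to 10.9 | 1.5 |
| Clustered; 10; 6 | 252 | 230 | 0.91 | 12.8 to 12.3 | 1.4 |
| Clustered; 15; 6 | 368 | 347 | 0.94 | 15.5 to 15.1 | 1.3 |

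If the chart's own retest variance (about 70, averaged over 15 rows) replaces the simulated noise, the even-spread ratio is 70/(70 + 102) = 0.41. This treats follow-up as baseline plus retest noise. The full range is therefore 0.41-0.94, a cut of about 5-60%. The 95% range of the imbalance contribution is ±1.96 × 1.3 = ±2.5 to ±1.96 × 2.8 = ±5.5 points.

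**Other WR endpoints.** The arcsine ratio is within about 0.01 of the raw-level ratio. For absolute change the ratio is 0.92-1.00, and for relative change 0.90-1.00. In the even, word-list-noise-only case, the planned change model already has a residual variance of 82, the same as the level model with the score added.

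**The case against.** The strongest reply is that the plan already contains the better analysis. SAP 7.3.3 models absolute change with the same covariates. Its residual variance is within 0-8% of what the measured score would give, and change is the form of the protocol's own endpoints. Percentage is simply twice the number of words, so 7.3.1 and 7.3.2 are one analysis shown twice. Adding the score makes them nearly repeat 7.3.3. All of this stands for the raw scale. It does not cover 7.3.6, which has no change-from-baseline version, and it does not stop the planned level comparisons from diverging from 7.3.3.

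The second reply is that the protocol sentence is qualified by appropriateness and defers to the SAP, and that the SAP does adjust for baseline in a coarse form. That also stands. A reader might infer a breach of the protocol, but the text supports only an unrecorded narrowing of a permissive statement.

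A reader might also infer that the change would halve the variance at no cost, or that the trial is losing the equivalent of a much larger sample. The documents support neither. Halving needs a correlation of about 0.86-0.89 and little real variation in change, whereas Protocol 8.1 describes earlier improvement in some patients only. On the raw scale, the information is largely recovered in 7.3.3.

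**Conclusion.** The point holds for the level endpoints in 7.3.1, 7.3.2 and 7.3.6. Their models omit a baseline measurement that the trial collects and that the protocol lists separately from the strata. The omission costs precision and lets within-category imbalance into the contrasts. The size is uncertain: a cut in residual variance of about 5-60%. With a true-change SD of 10 points and no extra session noise, the cut is 23-34% unless baselines are tightly clustered. Extra session noise lowers it, to 15% in the mid-weighted case. These figures rest on assumed baseline shapes and change SDs.

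It would be wrong to read this as a defect of the change analyses, where the gain is about 0-10%, or as bias in expectation, since randomization protects against that. The study is exploratory and its p-values are descriptive (SAP 7.1.4). What is affected is precision and the agreement between level and change results.

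**What to change.** In the models for SAP 7.3.1, 7.3.2 and 7.3.6:
- state that only post-baseline visits are responses. The SAP does not say whether Screening is one, and if it were, the same value would sit on both sides of the model;
- add the continuous Screening value of the analysed endpoint (arcsine scale for 7.3.6) and its interaction with visit;
- keep the 50% category and etiology, because both are stratification factors.

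The same term may be added to 7.3.3 and 7.3.4 for consistency. If the sponsor prefers the present model, the omission and its reason should be recorded in SAP Section 11.

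The cost is small but not nil. At a single visit it is one degree of freedom (about 90 to 89). With the interaction it is five parameters over the five post-baseline visits, or three at the Day 90 interim. The model also assumes a linear relation between baseline and follow-up, which should be checked with a residual plot. No new data are needed.
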